## **8.4 Analysis of secondary effectiveness outcomes**

Descriptive statistics (including extent of missing data) will be presented for all secondary effectiveness outcomes by trial arm at all time points at which they were collected, with changes in these outcomes, and changes in the estimated difference between groups over time illustrated graphically.

### **8.4.1 PEM Overall Questionnaire (14 items)**

Scores will be calculated using participant's responses to the items in parts 2 and 3 of the PEM questionnaire at 3, 6, 12 and 24 months post treatment. These will be presented descriptively by trial arm (complete cases only).

### **8.4.2 PEM Treatment Questionnaire (5 items)**

Scores will be calculated using participant's responses to the items in part 1 of the PEM questionnaire at 3, 6, 12 and 24 months post treatment. These will be presented descriptively by trial arm (complete cases only)

### **8.4.3 Unité Rhumatologique des Affections de la Main Scale**

Participants complete the URAM at baseline and 3, 6, 12 and 24 months post treatment and their responses used to generate a score between 0 and 45. Descriptive statistics for URAM scores will be reported by treatment group for each time point.

These scores will also be analysed using a similar covariance pattern model as used for the primary analysis, with the estimated differences in means (and two-sided 95% CIs) at each time point being reported. This model will include participants with at least one post-randomisation URAM score available (i.e. those with no post-randomisation URAM measurements will be excluded). Any missing baseline URAM scores will be imputed with predicted values via regression of the observed baseline URAM scores on observed baseline PEM scores and study reference joint (MCP or PIP). If baseline PEM score is also missing then missing baseline URAM scores will be imputed with predicted values via regression on the observed baseline MHQ scores and reference joint. If baseline MHQ score is also missing then missing baseline URAM scores will be imputed with the reference joint strata specific means.

The fitted model will be checked using the same techniques used for the primary analysis. Should any of these diagnostics suggest serious violation of the model assumptions, then the outcome data will be log transformed (with a value of 0.1 added to scores prior to transformation to allow for scores of 0) and the model refitted. If serious violation of the model assumptions persists, then the URAM scores at each post-treatment time point will be modelled in isolation, using a univariate mixed effect linear regression model, adjusting for allocation, reference joint type (the stratification factor) and baseline URAM score

as fixed effects, and centre as a random effect. Mixed effect generalised linear models with log link will be used if model assumptions remain severely violated.

If model assumptions remain severely violated for the univariate analyses of the URAM scores (with both identity and log links), then a semi-parametric analysis of the untransformed outcome measurements will be conducted using a mixed effect ordinal regression model with logit link. This model will include allocation, reference joint type (the stratification factor) and baseline URAM score as fixed effects, with random intercepts for centre. The fitted model will be used to derive estimates of the between group difference in means conditional on representative values of the other covariates (both levels of reference joint, mean of observed baseline URAM scores and marginalising over the random centre effects) together with 95% Wald CIs based on standard errors obtained via the delta method.

#### **8.4.4 Michigan Hand Questionnaire**

Participants complete the MHQ at baseline and 12 and 24 months post treatment, and their scores used to generate 6 scale scores and an overall score. Only MHQ data relating to the reference hand will be analysed and reported. Descriptive statistics for MHQ scores will be reported by treatment group for each time point.

The overall score for the reference hand at each time point will be analysed using a similar covariance pattern model as used for the primary analysis, with the estimated differences in means (and two-sided 95% CIs) at each time point being reported. This model will include participants with an MHQ score for at least one post-randomisation time point (i.e. those with no post-randomisation MHQ measurements will be excluded). Any missing baseline MHQ scores will be imputed with predicted values via regression of the observed baseline MHQ scores on observed baseline PEM scores and study reference joint (MCP or PIP). If baseline PEM score is also missing then missing baseline MHQ scores will be imputed with predicted values via regression on the observed baseline URAM scores and reference joint. If baseline URAM score is also missing then missing baseline MHQ scores will be imputed with the reference joint strata specific mean.

The fitted model will be checked using the same techniques used for the primary analysis. Should any of these diagnostics suggest serious violation of the model assumptions, then the outcome data will be log transformed (with a value of 0.1 added to scores prior to transformation to allow for scores of 0) and the model refitted. If serious violation of the model assumptions persists, then the MHQ scores at each post-treatment time point will be modelled in isolation, using a univariate mixed effect linear regression models, adjusting for allocation, reference joint type (the stratification factor) and baseline MHQ score as fixed effects, and centre as a random effect. Mixed effect generalised linear models with log link will be used if model assumptions remain severely violated.

If model assumptions remain severely violated for the univariate analysis MHQ scores (with both identity and log links), then a semi-parametric analysis using the untransformed outcome measurements will be conducted using a mixed effect ordinal regression model with logit link. This model will include allocation, reference joint type (the stratification factor) and baseline MHQ score as fixed effects, and

random intercepts for centre. The fitted model will be used to derive estimates of the between group difference in means conditional on representative values of the other covariates (both levels of reference joint, mean of observed baseline MHQ scores and marginalising over the random centre effects) together with Wald 95% CIs based on standard errors obtained via the delta method.

#### **8.4.5 Single Assessment Numeric Evaluation Score**

Participants are asked to provide a SANE score at baseline, 2 and 6 weeks post treatment and 3, 6, 12 and 24 months post treatment. These scores will be analysed using a similar covariance pattern model as used for the primary analysis, with the estimated differences in means (and two-sided 95% CIs) at each time point being reported. This model will include participants with a SANE score for at least one post-randomisation time point (i.e. those with no post-randomisation SANE measurements will be excluded). Any missing baseline SANE scores will be imputed with predicted values via regression of the observed baseline SANE scores on observed baseline PEM scores and study reference joint (MCP or PIP). If baseline PEM score is also missing then missing baseline SANE scores will be imputed with predicted values via regression on the observed baseline MHQ scores and reference joint. If baseline MHQ score is also missing then missing baseline SANE scores will be imputed with predicted values via regression on the observed baseline URAM scores and reference joint. If baseline URAM score is also missing then missing baseline SANE scores will be imputed with the reference joint strata specific means.

The fitted model will be checked using the same techniques used for the primary analysis. Should any of these diagnostics suggest serious violation of the model assumptions, then the outcome data will be log transformed (with a value of 0.1 added to scores prior to transformation to allow for scores of 0) and the model refitted. If serious violation of the model assumptions persists, then the SANE scores at each post-treatment time point will be modelled in isolation, using a univariate mixed effect linear regression models, adjusting for allocation, reference joint type (the stratification factor) and baseline SANE score as fixed effects, and centre as a random effect. Mixed effect generalised linear models with log link will be used if model assumptions remain severely violated.

If model assumptions remain severely violated for the univariate analysis SANE scores (with both identity and log links), then a semi-parametric analysis of the untransformed outcome measurements will be conducted using a mixed effect ordinal regression model with logit link. This model will include allocation, reference joint type (the stratification factor) and baseline SANE score as fixed effects, with random intercepts for centre. The fitted model will be used to derive estimates of the between group difference in means conditional on representative values of the other covariates (both levels of reference joint, mean of baseline SANE score and marginalising over the random centre effects) together with Wald 95% CIs based on standard errors obtained via the delta method.

#### **8.4.6 Overall hand assessment**

Participants are asked a global question about the problems they experience with the hand that was treated in comparison to before treatment. Responses are given on a 7 item ordered categorical scale from Terrible to Cured. Responses at each time point will first be summarised descriptively and

graphically by treatment group. Responses to the Overall Hand Assessment at 12 months will be analysed using a mixed effect proportional odds logistic regression model, with randomised group, reference joint and baseline PEM score included as fixed effects and centre as a random effect. This model will include all participants with a non-missing overall hand assessment response at 12 months post-treatment. Missing baseline PEM scores will be imputed using predicted values via regression of the observed baseline PEM scores on observed baseline MHQ scores and reference joint (MCP or PIP). If the MHQ score is also missing then missing baseline PEM scores will be imputed using predicted values via regression of the observed baseline PEM scores on the observed baseline URAM scores and reference joint. If the URAM score is also missing then missing baseline PEM scores will be imputed with the reference joint strata specific mean. The estimated odds ratio for allocation (and two-sided 95% CI) will be reported. This model will also be used to derive the absolute difference between groups in the probability of a response of either “Cured” or “Much better”, at representative values of the fixed effect covariates (mean of observed baseline PEM scores both levels of reference joint and marginalising over the random centre effects), together with Wald 95% CIs based on delta method standard errors.

#### **8.4.7 Recurrence**

Recurrence will be defined in a binary manner (recurred or not recurred) at 6, 12 and 24 months post-treatment. Recurrence at the 6 month follow up is defined as an increase in passive extension deficit of the reference joint of 6° since the 3 month post treatment follow up. Recurrence at 12 and 24 months is defined as an increase in passive extension deficit of the reference joint of 20° since the 3 month post treatment follow up. These binary outcomes will be modelled using mixed effect logistic regression models adjusting for study reference joint (MCP or PIP), study reference digit, baseline PEM score and baseline passive extension measurement as fixed effects with centre as a random effect. These models will include all participants for whom the relevant (i.e. month 6 or month 12) binary indicator of recurrence can be derived using the available data. If perfect prediction occurs due to empty strata at some covariate combinations, then participants with study reference digit indicated as middle, index or thumb will be pooled so that reference digit becomes a three category covariate (little, ring, other). If the issue persists, then the term for study reference digit will be dropped from the model. If the baseline PEM score and/or baseline passive extension measurement is missing, then they will be imputed using predicted values via regression of the observed values on observed baseline MHQ scores and reference joint (MCP or PIP). If the MHQ score is also missing, then missing baseline PEM scores and/or baseline passive extension measurements will be imputed using predicted values via regression of the observed values on the observed baseline URAM scores and reference joint. If baseline URAM score is also missing then missing baseline PEM scores and/or baseline passive extension measurements will be imputed with the reference joint strata specific means. For both analyses, the estimated odds ratios for allocation (and two-sided 95% CIs) will be reported. This model will also be used to derive the absolute differences in risk of recurrence (together with two-sided 95% CIs) at representative values of the covariates (mean of the continuous covariates, both levels of reference joint, two levels of reference digit (ring or little) and marginalising over the centre random effects). We will also test composite null hypotheses about the absolute difference in incidence of recurrence at 12

and 24 months post-treatment. Specifically we will report one-sided p-values from four Wald tests of  $H_0: d \geq 10\%$  , where  $p < 0.025$  indicates statistical significance, and  $d = \Pr(\text{Recurrence} \mid \text{Collagenase}, X) - \Pr(\text{Recurrence} \mid \text{Surgery}, X)$  for the four covariate patterns  $X$  outlined above (MCP + Ring, MCP + Little, PIP + Ring, PIP + Little).

Due to the Coronavirus pandemic, a substantial proportion of participants were followed up remotely at 3, 6, 12 and 24 months post-treatment, and did not have goniometric measurements taken. Missingness due to remote follow up, as well as attrition, mean a substantial proportion of the post-treatment goniometric measurement data will be missing. The proportion of missing data at each time point will be summarised by randomised group, as will the available reasons this missing data. The principal analyses of recurrence outlined above (based on the available goniometric measurements) will be repeated using two alternative analysis sets. The first analysis set will supplement the available goniometric measurements with measurements obtained using photographs taken by clinical investigators. If photographs taken by the clinical investigators are not available, then measurements obtained using photographs taken by the participant will be used (note this would include photographs submitted by participants in the photography sub-study, as well as photographs submitted by non-sub-study participants who could not attend clinic visits due to the pandemic). The second analysis will use the multiply imputed dataset(s) generated as part of the analyses specified in Section 8.3.1. Both analysis sets will be analysed using the same models used for the analysis of the available goniometric measurements, with estimates and tests being reported analogously.

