### 5.6.1 Recurrence

Recurrence at 6 months is defined as a change in extension deficit (measured as passive extension) of the reference joint of 6° or greater between 3 and 6 months post treatment. Recurrence at 12 months is defined as a change in extension deficit (measured as passive extension) of 20° or greater between 3 and 12 months post treatment [6]. This definition will be used to compare recurrence in each arm at 6 and 12 months post treatment.

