## 8. Analysis

All analyses will be conducted following intention to treat principles on a locked dataset using the latest available version of Stata. Continuous data will be summarised in terms of the non-missing sample size, mean, standard deviation, median, interquartile range and range, and categorical data will be summarised in terms of frequencies and proportions. The primary objective of the analysis is to investigate whether there is sufficient evidence to reject the hypothesis that outcomes (as measured by the 11 items in part 2 of the PEM) at 12 months post-treatment among patients randomised to collagenase are inferior to those of patients randomised to surgery, assuming a non-inferiority margin of 6 points. This assessment will be primarily based on whether the upper limit of the two-sided 95% CI for the difference between treatments at 12 months post treatment obtained from the primary analysis model (see Section 8.2) is greater than 6. One of the key secondary objectives is to compare the extent to which the correction achieved following treatment is maintained over the 12 months following treatment. This will be assessed by comparing rates of recurrence at 12 months post-treatment, where recurrence at 12 months is defined as a reduction in passive extension of 20 degrees between 3 and 12 months post-treatment (see Section 5.6.1). We will investigate whether there is sufficient evidence to reject the hypothesis that collagenase is inferior to surgery in terms of rates of recurrence at 12 months post-treatment, assuming a non-inferiority margin of 10%. This assessment will be based on whether the upper limits of the two-sided 95% CIs for the absolute differences in recurrence obtained from the fitted model (see Section 8.4.7) are less than 10%, and associated one-sided hypothesis tests of  $H_0: d \geq 10\%$ , where  $d = \Pr(\text{Recurrence} \mid \text{Collagenase}, X) - \Pr(\text{Recurrence} \mid \text{Surgery}, X)$  for various pre-specified representative covariate patterns  $X$ .

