#### **8.4.12 Further treatment**

At each of the 3, 6, 12 and 24 month post treatment follow up visits, data pertaining to further treatments of the reference digit since the last visit are collected. If participants undergo further collagenase injection, limited fasciectomy surgery, dermofasciectomy or percutaneous needle fasciotomy to the reference digit at any point during follow up, then this will be counted as further treatment. Ongoing hand therapy and/or physiotherapy appointments to treat chronic regional pain syndrome, stiffness, swelling or scar problems, will also be considered further treatment. Participants who undergo more than six outpatient follow up visits for hand therapy and/or physiotherapy will have the details of these appointments reviewed on an individual basis to determine whether this extended duration of therapy should be considered to be further treatment or routine care.

The number of participants receiving further treatment to the reference digit will be reported by allocation, and the unadjusted odds ratio and risk difference will be reported (together with two-sided 95% CIs). The proportion of participants undergoing further treatment to the reference digit will be modelled using a mixed effects logistic regression model. This model will include allocation, study reference joint type (MCP or PIP), study reference digit and baseline PEM score as fixed effects with clustering by centre modelled using a random intercept. If perfect prediction occurs due to empty strata for some covariate combinations, then participants with study reference digit indicated as middle, index or thumb will be pooled so that reference digit becomes a three category covariate. If the issue persists, then the term for study reference joint will be dropped from the model. If baseline PEM score is missing then it will be imputed using predicted values via regression on baseline MHQ score. If MHQ score is also missing then baseline URAM score will be used. If baseline URAM score is also missing then mean imputation will be used. This model will be used to derive adjusted odds ratios and risk differences for allocation (together with two-sided 95% CIs).

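### Recurrence (SAP 8.4.7) has no rule for further procedures after 3 months, so a recurrence that is corrected again can be scored as no recurrence in the 10% non-inferiority comparison

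*SAP*

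**What the plan says.** Section 8 of the SAP gives recurrence a prominent place: "One of the key secondary objectives is to compare the extent to which the correction achieved following treatment is maintained over the 12 months" after treatment. It sets a non-inferiority margin of 10 percentage points for the absolute difference, collagenase minus surgery. Section 8.4.7 adds four one-sided Wald tests, one per covariate pattern, at 12 and at 24 months, each judged at 0.025.

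The outcome is defined by angle only. In 8.4.7: "Recurrence at the 6 month follow up is defined as an increase in passive extension deficit of the reference joint of 6" degrees, and "Recurrence at 12 and 24 months is defined as an increase in passive extension deficit of the reference joint of 20" degrees, both counted from the 3-month visit. Section 5.6.1 gives the 12-month version as a "change in extension deficit (measured as passive extension) of 20° or greater between 3 and 12 months post treatment".

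On who is analysed, 8.4.7 says: "These models will include all participants for whom the relevant (i.e. month 6 or month 12) binary indicator of recurrence can be derived" from the data available. Participants who were treated again are neither excluded nor recoded.

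Further treatment is a separate outcome in 8.4.12: "If participants undergo further collagenase injection, limited fasciectomy surgery, dermofasciectomy or percutaneous needle fasciotomy to the reference digit at any point during follow up", this counts as further treatment, and some continuing hand therapy counts too. Section 5.8 records the timing and details of each further procedure and whether it concerned the reference hand or finger. Table 3 in 8.3.1 lists the same four procedures as a yes/no variable in the imputation model. Nothing links any of this to the recurrence score.

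**The concern.** The stated purpose of the comparison is to see whether correction is maintained. A joint that lost its correction and was corrected again did not maintain it, yet the angle at the visit can show it as a success. The comparison is a non-inferiority test, so the usual effect of such misclassification, a smaller difference between arms, works in the direction that favours the new treatment. Section 8.3.2 recognises an anti-conservative bias of this type for the primary outcome, but 8.4.7 does not consider it for recurrence. At stake is the claim on recurrence at 12 months, and again at 24 months, when there has been more time for re-treatment. The primary conclusion on the PEM is not touched.

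**Working it through.** **Step 1: follow one participant through the rule.** The deficit rises by 20 degrees or more after the 3-month visit, the digit is treated again, and the 12-month visit follows. There are three outcomes:
- measured at least 20 degrees above the 3-month value: coded as recurred;
- measured less than 20 degrees above it: coded as not recurred;
- not measured: no indicator can be derived, so the participant drops out of the principal analysis.

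The gap lies in the second case.

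**Step 2: does another part of the SAP close it?**
- The two repeat analyses in 8.4.7 (photograph-supplemented and multiply imputed) use the same models and give no new definition.
- Further treatment in Table 3 only helps to impute missing values. An angle observed after re-treatment stays as measured.
- The acceptance of later treatment as part of the strategy in 8.3.3 is written for the complier-average analysis of the 12-month PEM.
- Intention to treat (Section 8) fixes the groups compared, not the scoring of an angle taken after re-treatment.
- The logistic and Cox analyses in 8.4.12 would show an imbalance in re-treatment but do not alter the recurrence estimate or its test.

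**Step 3: the plan's own sizing.** The only sizing is for the PEM (Section 3). With margin 6, SD 22, one-sided 2.5% and 90% power, n = 2 × 22² × (1.960 + 1.282)² / 6² gives 283 per arm. The t-test calculation gives 284, that is 568 in total, and 568 / 0.8 = 710. The figure reproduces. It says nothing about recurrence, so 284 per arm is borrowed below only as a scale.

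**Step 4: effect on the difference.** All rates here are assumptions, because the SAP gives none. Let p be the true recurrence rate in an arm, and r the share of its recurrers who are corrected again and measure below the threshold at the visit. Then:

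observed rate = p × (1 − r)

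observed d = (pC − pS) − (pC × rC − pS × rS)

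The difference is understated whenever pC × rC exceeds pS × rS. If pC > pS, any positive rC that is at least as large as rS is enough.

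Chance of declaring non-inferiority = Φ((0.10 − d) / SE − 1.96), where SE = √[(pC(1 − pC) + pS(1 − pS)) / n] on the observed rates. This is an unadjusted approximation to the SAP's model-based tests.

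True rates 20% v 10%, so true d is exactly at the margin:

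| Corrected share, collagenase v surgery | Observed rates | Observed d (points) | Chance, 284 per arm | Chance, 142 per arm |
|---|---|---|---|---|
| 0% v 0% | 20% v 10% | 10 | 2.5% | 2.5% |
| 20% v 20% | 16% v 8% | 8 | 11% | 7.5% |
| 30% v 10% | 14% v 9% | 5 | 47% | 26% |
| 50% v 10% | 10% v 9% | 1 | 96% | 74% |
| 10% v 30% | 18% v 7% | 11 | 1% | 1% |

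The 142 column assumes that half the measurements are missing. Section 8.4.7 expects a substantial proportion to be missing but gives no figure.

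**Step 5: other base rates, 284 per arm.** With 20% corrected in both arms, d is 8 points at true rates of 30% v 20% and of 15% v 5%, and the chance is 8.7% and 14.2%. With 10% v 30% corrected at 15% v 5%, the two terms cancel (0.15 × 0.10 = 0.05 × 0.30) and there is no bias. With true rates of 22% v 10%, beyond the margin, and 30% v 10% corrected, d falls from 12 to 6.4 points and the chance rises from 0.4% to 26%.

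**Step 6: typical upper confidence limits at 20% v 10%, 284 per arm.**
- No correction: SE = √(0.25 / 284) = 2.97 points, so 10 + 1.96 × 2.97 = 15.8.
- 20% v 20%: SE = √(0.208 / 284) = 2.71, so 8 + 5.3 = 13.3.
- 30% v 10%: SE = √(0.2023 / 284) = 2.67, so 5 + 5.2 = 10.2.

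The limit moves toward 10 but does not necessarily cross it.

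**The case against.** Scoring the joint as it stands at the visit, whatever happened before, is a recognised treatment-policy choice and fits intention to treat. Re-treatment is not concealed either: 8.4.12 reports an adjusted odds ratio and risk difference, with Kaplan-Meier and Cox analyses. That is fair, but the SAP does not state this choice for recurrence, and a separate table does not correct a non-inferiority test.

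A reader might infer that every re-treated participant is coded as not recurred. The SAP does not support that. It happens only if the joint is measured and the deficit is back below the threshold; an unmeasured participant has no indicator.

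A reader might also infer that the rule must favour collagenase, or would carry a failing result past the margin. Neither follows. The direction depends on re-treatment rates in each arm, which the SAP does not give, and Step 6 shows plausible shifts that still leave the typical limit above 10.

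The objection is strongest against replacing the principal definition. Further treatment is defined in 8.4.12 for the digit, whereas recurrence concerns the reference joint. A procedure may be for another joint, or for contracture never corrected by 3 months. If, say, 8% v 3% are re-treated and 80% of them had recurred, the missing difference is (0.08 − 0.03) × 0.8 = 4 points, but coding all of them as recurred adds 5, an overshoot of 1 point against collagenase. The measured definition, which 5.6.1 supports with a cited reference, should therefore stay.

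Lastly, 5.6.1 speaks of a *change*, which read literally would include improvement. Section 8 (a reduction in passive extension) and 8.4.7 (an increase in deficit) settle the direction, so this is clerical.

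**Conclusion.** The gap is real. Recurrence is scored from angle alone, no rule covers procedures after 3 months, and a recurrence corrected before the visit can be coded as none in a key secondary non-inferiority comparison at 12 and 24 months. The same definition applies at 6 months, where no non-inferiority test is planned. The bias tends toward non-inferiority when true recurrence is higher after collagenase and its recurrers are corrected again at least as often as those after surgery; it can vanish or reverse otherwise. Its size cannot be known from the SAP. In the illustration with equal correction of 20%, it is 2 points (10 to 8), with the chance of declaring non-inferiority at the margin rising from 2.5% to about 11%. That rests on assumed rates, 284 per arm and an unadjusted test. The point supports an added analysis and a joint reading of the two, not removal of the measured definition.

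**What to change.** In 8.4.7, add a pre-specified composite analysis with the same models and tests:
- Count as recurred anyone who, after the 3-month visit and before the 6, 12 or 24 month assessment, had one of the four procedures listed in 8.4.12 and Table 3 for contracture of the reference joint, or of the reference digit where the joint is not recorded.
- Apply this whatever angle is then measured, and also when it is missing.
- Do not count hand therapy or physiotherapy, which 8.4.12 can include as further treatment.
- Report the composite beside the measured-only analysis, and claim non-inferiority on recurrence only if both agree.

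As a clerical matter, align *change* in 5.6.1 with *increase* in 8.4.7.

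The cost is a few lines of SAP text and one derivation from data already collected under 5.8. The composite may over-count procedures for another joint or for contracture not corrected by 3 months, which is why the measured-only analysis is kept. It also gives a score to participants re-treated in the window who have no measurement.
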